### For Grade 1:

- Monitor and closely follow up in 2 to 4 days for clinical

Grade 1 - No dose modifications.

(mild pain)

#### Grade 2

#### (moderate pain associated with weakness; pain limiting instrumental activities of daily living [ADLs])

Hold study drug/study regimen dose until resolution to Grade <1.

 Permanently discontinue study drug/study regimen if it does not resolve to Grade ≤1 within 30 days or if there are signs of respiratory insufficiency. symptoms and initiate evaluation as clinically indicated.

- Consider Neurology consult.
- Consider, as necessary, discussing with the study physician.

#### For Grade 2:

- Monitor symptoms daily and consider hospitalization.
- Obtain Neurology consult, and initiate evaluation.
- Consider, as necessary, discussing with the study physician.
- If clinical course is rapidly progressive (particularly if difficulty breathing and/or trouble swallowing), promptly start IV methylprednisolone 2 to 4 mg/kg/day systemic steroids along with receiving input from Neurology consultant
- If clinical course is *not* rapidly progressive, start systemic steroids (e.g., prednisone 1 to 2 mg/kg/day PO or IV equivalent); if no improvement within 3 to 5 days, continue additional work up and start treatment with IV methylprednisolone 2 to 4 mg/kg/day
- If after start of IV methylprednisolone at 2 to 4 mg/kg/day there is no improvement within 3 to 5 days, consider start of immunosuppressive therapy such as TNF inhibitors (e.g., infliximab at 5 mg/kg every 2 weeks). Caution: It is important to rule out sepsis and refer to infliximab label for general guidance before using infliximab.
- Once the patient is improving, gradually taper steroids over ≥28 days and consider prophylactic antibiotics, antifungals, or anti-PJP treatment (refer to current NCCN guidelines for treatment of cancer-related infections [Category 2B recommendation]).a

#### For Grade 3 or 4 (severe or life-threatening events):

- Monitor symptoms closely; recommend hospitalization.
- Obtain Neurology consult, and complete full evaluation.
- Consider, as necessary, discussing with the study

Grade 3 or 4	For Grade 3:
(pain associated wit	h Hold study drug/study regimen dose
severe weakness; limiting self-care	until resolution to Grade $\leq 1$ .
ADLs)	Permanently discontinue study

drug/study regimen if Grade 3 imAE	physician.	
does not resolve to Grade $\leq 1$ within 30 days or if there are signs of	
 
Promptly start IV methylprednisolone 2 to 4 mg/kg/day systemic steroids along with receiving input from Neurology consultant.
 
	

 
respiratory insufficiency.
 
For Grade 4:
 
Permanently discontinue study drug/study regimen.
 
	
 
If after start of IV methylprednisolone at 2 to 4 mg/kg/day there is no improvement within 3 to 5 days, consider start of immunosuppressive therapy such as TNF inhibitors (e.g., infliximab at 5 mg/kg every 2 weeks). Caution: It is important to rule out sepsis and refer to infliximab label for general guidance before using infliximab.
 
	
	
 
Consider whether patient may require IV IG, plasmapheresis.
 
	
	
 
Once the patient is improving, gradually taper steroids over ≥28 days and consider prophylactic antibiotics, antifungals, or anti-PJP treatment (refer to current NCCN guidelines for treatment of cancer-related infections [Category 2B recommendation]).a
 
	

aASCO Educational Book 2015 "Managing Immune Checkpoint Blocking Antibody Side Effects" by Michael Postow MD.

bFDA Liver Guidance Document 2009 Guidance for Industry: Drug Induced Liver Injury – Premarketing Clinical Evaluation.

AChE Acetylcholine esterase; ADL Activities of daily living; AE Adverse event; ALP Alkaline phosphatase test; ALT Alanine aminotransferase; AST Aspartate aminotransferase; BUN Blood urea nitrogen; CT Computed tomography; CTCAE Common Terminology Criteria for Adverse Events; ILD Interstitial lung disease; imAE immune-mediated adverse event; IG Immunoglobulin; IV Intravenous; GI Gastrointestinal; LFT Liver function tests; LLN Lower limit of normal; MRI Magnetic resonance imaging; NCI National Cancer Institute; NCCN National Comprehensive Cancer Network; PJP *Pneumocystis jirovecii* pneumonia (formerly known as *Pneumocystis carinii* pneumonia); PO By mouth; T3 Triiodothyronine; T4 Thyroxine; TB Total bilirubin; TNF Tumor necrosis factor; TSH Thyroid-stimulating hormone; ULN Upper limit of normal.

Severity Grade of the Event (NCI CTCAE version 4.03)	Dose Modifications	Toxicity Management
Any Grade	General Guidance	For Any Grade:
		
 
Manage per institutional standard at the discretion of investigator.
 

		
 
Monitor patients for signs and symptoms of infusion-related reactions (e.g., fever and/or shaking chills, flushing and/or itching, alterations in heart rate and blood pressure, dyspnea or chest discomfort, or skin rashes) and anaphylaxis (e.g., generalized urticaria, angioedema, wheezing, hypotension, or tachycardia).
 

Grade 1 or 2	For Grade 1:	For Grade 1 or 2:
	The infusion rate of study drug/study regimen may be decreased by 50% or temporarily interrupted until	
 
Acetaminophen and/or antihistamines may be administered per institutional standard at the discretion of the investigator.
 

	resolution of the event.	
 
Consider premedication per institutional standard prior to subsequent doses.
 

	For Grade 2:	- Steroids should not be used for routine premedication of
	The infusion rate of study drug/study regimen may be decreased 50% or temporarily interrupted until resolution of the event.	Grade $\leq 2$ infusion reactions.
	Subsequent infusions may be given at 50% of the initial infusion rate.	
Grade 3 or 4	For Grade 3 or 4:	For Grade 3 or 4:
	Permanently discontinue study drug/study regimen.	
 
Manage severe infusion-related reactions per institutional standards (e.g., IM epinephrine, followed by IV diphenhydramine and ranitidine, and IV glucocorticoid).
 

**Infusion-Related Reactions** 

CTCAE Common Terminology Criteria for Adverse Events; IM intramuscular; IV intravenous; NCI National Cancer Institute.

Severity Grade of the Event (NCI CTCAE version 4.03)	Dose Modifications	Toxicity Management
Any Grade	Note: Dose modifications are not required for AEs not deemed to be related to study treatment (i.e., events due to underlying disease) or for laboratory abnormalities not deemed to be clinically significant.	Treat accordingly, as per institutional standard.
Grade 1	No dose modifications.	Treat accordingly, as per institutional standard.
Grade 2	Hold study drug/study regimen until resolution to ≤Grade 1 or baseline.	Treat accordingly, as per institutional standard.
Grade 3	Hold study drug/study regimen until resolution to ≤Grade 1 or baseline.	Treat accordingly, as per institutional standard.
	For AEs that downgrade to ≤Grade 2 within 7 days or resolve to ≤Grade 1 or baseline within 14 days, resume study drug/study regimen administration. Otherwise, discontinue study drug/study regimen.	
Grade 4	Discontinue study drug/study regimen (Note: For Grade 4 labs, decision to discontinue should be based on accompanying clinical signs/symptoms, the Investigator's clinical judgment, and consultation with the Sponsor.).	Treat accordingly, as per institutional standard.

# Non-Immune-Mediated Reactions

Note: As applicable, for early phase studies, the following sentence may be added: "Any event greater than or equal to Grade 2, please discuss with Study Physician."

AE Adverse event; CTCAE Common Terminology Criteria for Adverse Events; NCI National Cancer Institute.

#### 4.5 **Duration of Therapy**

Patients on all arms will remain on study as long as there is no disease progression for up to 24 months or until any of the following occur:

- Disease progression
- Development of an inter-current illness that prevents further administration of treatment
- Unacceptable adverse event(s)
  - See section on dose modifications: Treatment delay of > 4 weeks due to treatment related toxicities.
  - Protracted (>2 weeks) medically concerning grade 2 cardiac, pulmonary, renal, gastrointestinal, skin, or CNS toxicities.
- The treating investigator determines that the patient should be taken off treatment for any reason (i.e. changes in condition, inability to comply with study treatment or procedures).

#### 4.6 Duration of Follow Up

All subjects will be followed for survival for up to 2 years/24 months from stopping study treatment. Subjects who decline to return to the site for evaluations will be offered follow-up by phone every 8-16 weeks as an alternative.

Note that patients who discontinue treatment permanently for any reason other than progression will be followed for evidence of tumor response and disease status.

Any patient who withdraws their consent, will be considered as an early discontinuation, and may be replaced if this occurs before they have received the first dose of treatment. Patients who withdraw consent but receive at least one dose of treatment will be evaluable for toxicity even if they are not fully evaluable for response. The accrual goal has been set to allow up to 45 patients to be enrolled in order to allow for early discontinuations.

If a patient withdraws consent, no further treatment or study-specific testing will be completed. The primary reason for a patient's withdrawal from the study is to be recorded in the source documents. All patients will be followed until death or 2 years/24 months from stopping treatment.

Subjects who are permanently discontinued from further receipt of investigational product, regardless of the reason (withdrawal of consent, due to an AE, other), will be identified as having permanently discontinued treatment.

Subjects who are permanently discontinued from receiving investigational product will be followed for safety for 30 days post last-dose visit including the collection of any protocol-specified blood specimens, unless consent is withdrawn or the subject is lost to follow-up or enrolled in another clinical study. If a subject is enrolled in another clinical study, they will be followed until all AEs are resolved or stable. If enrolled onto another clinical study, it is not necessary to follow the subject for survival or progression.

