## 1.0 INTRODUCTION – BACKGROUND & RATIONALE

### 1.1 Disease Background

Malignant gliomas are unfortunately a uniformly fatal tumor in most cases. Despite aggressive surgery, radiation treatment (RT) and chemotherapy at initial diagnosis these tumors almost always recur. Patients seen in academic centers are often recruited to clinical trials that utilize novel agents in combination with standard therapy in newly diagnosed patients or those with recurrent disease. We know that gliomas are highly vascular tumors and there is data from the "Brain Trial" and "NIH trial" showing high response rates and reasonably good progression free survival at 6 months for patients treated with bevacizumab.  Unfortunately, data using bevacizumab in newly diagnosed patients with GBM did not provide any survival benefit but it did improve PFS at 6 months in the AVAGLIO trial but not RTOG trial. 

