#### 4.7 Removal of Subjects from Study Treatment and/or Study as a Whole

Patients can be taken off the study treatment and/or study as a whole at any time at their own request, or they may be withdrawn from study treatment at the discretion of the investigator for safety, behavioral or administrative reasons. The reason(s) for discontinuation from study treatment must be clearly documented on the appropriate eCRF and may include:

- Patient voluntarily withdraws from treatment (follow-up permitted)
- Patient withdraws consent (no follow-up permitted)
- Patient is unable to comply with protocol requirements
- Patient demonstrates disease progression

- Patient experiences unacceptable toxicity
  - See section on dose modifications: Treatment delay of > 4 weeks due to treatment related toxicities.
  - Protracted (>2 weeks) medically concerning grade 2 cardiac, pulmonary, renal, gastrointestinal, skin, or CNS toxicities.
- Grade  $\geq$  3 infusion reaction
- Treating physician determines that continuation on the study would not be in the patient's best interest
- Subject is determined to have met one or more of the exclusion criteria for study participation at study entry and continuing investigational therapy might constitute a safety risk
- Patient becomes pregnant or wants to become pregnant
- Patient develops a second malignancy that requires treatment which would interfere with this study
- Patient becomes lost to follow-up (LTF)
- Initiation of alternative anticancer therapy including another investigational agent
- Confirmation of PD and investigator determination that the subject is no longer benefiting from treatment with MEDI4736

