-  During adjuvant treatment, one cycle is defined as 4 weeks for patients on Arms 1 and 2. For patients on Arm 3, please refer to the schedule outlined in footnote #14.
-  Blood samples will be collected for various research tests at 1 st pre-operative treatment, day of surgery, C1D1 and at each adjuvant treatment imaging visits (i.e. every 2 cycles or 8 weeks):
  - a) 10ml blood in one 10ml Sodium heparin tube: To be collected and processed by the [name] lab for peripheral blood lymphocytes (PBLs).
  - b) 8m (2x4ml) blood in two 5ml EDTA (purple top) tubes: To be collected and processed by the [name] lab for gene expression profile using mononuclear cells.
  - c) 10ml blood in one 10ml red top tube: To be collected and processed by the [name] lab for analysis of tryptophan catabolites and cytokines.
  - Please refer to section 9.0 and laboratory manual for more details
-  Any patient who undergoes further surgery will have the option to use their tumor tissue for research to understand the immunologic changes occurring at the time of presumed drug failure. Please refer to Section 9 and laboratory manual for details.
-  Follow up for disease progression (if not already documented) and survival will occur every 8-16 weeks once off treatment. All patients will be followed until death or 2 years/24 months from stopping treatment.
-  Patients enrolled on Arm 1 will receive tremelimumab monotherapy: one 75 mg dose IV on day 1 (+/- 2 days) per cycle (every 4 weeks) up to 24 months.
-  Patients enrolled on Arm 2 will receive MEDI4736 monotherapy: one 750 mg dose IV on days 1 and 15 (+/- 2 days allowed for each) per cycle (every 2 weeks) up to 24 months.
-  Patients enrolled on Arm 3 will receive combination therapy (tremelimumab 75 mg + MEDI4736 750 mg) according to the following schedule: Tremelimumab will be administered IV every 4 weeks (Day 1 of each cycle) and MEDI4736 750mg every 2 weeks (Day 1 and Day 15 of each cycle) until the patients have received 7 doses of Tremelimumab and 14 doses of MEDI4736. Thereafter, from Cycle 7 (Week 25), Tremelimumab will be given every 12 weeks (+/-7 days) and MEDI4736 will be given every 2 weeks (+/- 2 days) until permanent discontinuation criteria (e.g. disease progression) is met. If there is no progression of disease, they will continue on treatment for up to 24 months.

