### 7.2.2 Severity of AEs

All adverse events will be graded according to the NCI Common Terminology Criteria for Adverse Events (CTCAE) version 4.0. The CTCAE v4.03 is available at http://ctep.cancer.gov/reporting/ctc.html

If no CTCAE grading is available, the severity of an AE is graded as follows:

- Mild (grade 1): the event causes discomfort without disruption of normal daily activities.
- Moderate (grade 2): the event causes discomfort that affects normal daily activities.
- Severe (grade 3): the event makes the patient unable to perform normal daily activities or significantly affects his/her clinical status.
- Life-threatening (grade 4): the patient was at risk of death at the time of the event.
- Fatal (grade 5): the event caused death.

All deaths that occur during the study, or within the protocol-defined 90-day post-last dose of study drug safety follow-up period must be reported as follows:

• Death that is clearly the result of disease progression should be documented but should not be reported as an SAE.

Where death is not due (or not clearly due) to progression of the disease under study, the AE causing the death must be reported as a SAE within **24 hours** (see Section 7.3.3 for further details). The report should contain a comment regarding the co-involvement of progression of disease, if appropriate, and should assign main and contributory causes of death.

Deaths with an unknown cause should always be reported as a SAE. Deaths that occur following the protocol-defined 90-day post-last-dose of study drug safety follow-up period will be documented as events for survival analysis, but will not be reported as an SAE.

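### Section 4.6 lets survival follow-up stop once a patient joins another study, an exception schedule footnote 11 does not carry; where used, it can informatively censor secondary overall survival, by an amount and in a direction the documents do not settle

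*Combined protocol and SAP*

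**What the plan says.** Section 4.6 opens with a general rule: "All subjects will be followed for survival for up to 2 years/24 months from stopping study treatment". It later repeats that all patients are followed until death or 24 months after stopping treatment, and it offers phone follow-up every 8-16 weeks to those who will not return to the site. Its final lines deal with patients who join another trial. For safety, "If a subject is enrolled in another clinical study, they will be followed until all AEs are resolved or stable". For outcomes, "If enrolled onto another clinical study, it is not necessary to follow the subject for survival or progression".

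Footnote 11 to the Section 5.2 schedule reads "Follow up for disease progression (if not already documented) and survival will occur every 8-16 weeks once off treatment", and again sets death or 24 months as the end point for all patients. It has no exception for entry to another study. Section 7.2.2, a reporting passage, says of deaths more than 90 days after the last dose that they "will be documented as events for survival analysis, but will not be reported as an SAE", also without exception.

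OS is a secondary endpoint (Sections 2.2.3 and 6.2). It runs from first dose to death from any cause, in patients who were dosed and operated on. Section 10.3 analyses it by Kaplan-Meier, censors patients alive at last follow-up then, and relates immunologic changes to survival outcomes by Cox regression. Neither the censoring rule nor any sensitivity analysis mentions entry to another study.

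**The concern.** Staff working from Section 4.6 may stop asking whether a patient is alive once that patient joins another trial. Staff working from footnote 11 would carry on. The same patient can therefore give a complete or a truncated survival time, depending on which page is followed.

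Kaplan-Meier and Cox methods assume that a censored patient has the same future risk as those still under observation at that time. In recurrent glioblastoma, entry to a new trial would usually be prompted by progression, when the risk of death rises. Censoring then removes patients just as their hazard goes up and leaves a risk set richer in patients who have not progressed. That pushes the curve upward. If those who join are fitter than other progressed patients, censoring removes the better prognoses and pushes it downward. Both forces can act together.

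The trigger is plausible. Section 1.1 notes that "Patients seen in academic centers are often recruited to clinical trials that utilize novel agents", and Section 4.7 lists "Initiation of alternative anticancer therapy including another investigational agent" among the reasons for coming off treatment. Neither gives a frequency.

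**Working it through.** **Plan figures.** There is no OS figure to reproduce. The 31% precision and the 1.25 SD difference in Section 10.3 concern the responder proportion and mean change, not survival.

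**Step 1: the text.** The general rule in 4.6, its repetition there and footnote 11 all say every patient. The last sentence of 4.6 is a permission limited to patients in another study. The 10.3 rule then fixes the censoring date at last follow-up. That date is not necessarily the date of entry, because adverse-event contact (4.6) and death reporting for 90 days after last dose (7.2.2) may extend it.

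**Step 2: worst-case width, with no assumption on entry or survival.** If *m* of *n* OS-evaluable patients have status unknown before 12 months, and all others are known, 12-month survival can lie anywhere in a range of width *m/n*.

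- n = 10 (the evaluable target per arm): 1/10 = 10 points; three lost, 30 points.
- n = 15 (the accrual cap per arm): 1/15 = 6.7 points; three lost, 20 points.

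**Step 3: an illustration with assumed inputs.** The documents give none of these:

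- a share *p* of 10-30% enters another trial at progression;
- median time to progression is 2-4 months (exponential, rate *a* = ln 2/median);
- median survival after progression is 4-8 months (rate *b*);
- entrants live *r* = 0.5-2 times as long after progression as non-entrants (rate *b/r*).

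Let U = exp(-at) be the proportion not yet progressed and V(b) = a/(b-a) × [exp(-at) - exp(-bt)] the proportion progressed and alive (a·t·exp(-at) when a = b).

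- True survival: S = U + (1-p)V(b) + pV(b/r).
- Large-sample Kaplan-Meier with entrants censored at progression: exp{-∫ b(1-p)V(b) / [U + (1-p)V(b)] dt}.

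*Worked case:* both medians 4 months, p = 0.3, t = 12. Then at = 12 × ln 2/4 = 2.079 and exp(-at) = 0.125.

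- Non-entrants: 0.125 × (1 + 2.079) = 0.385.
- Kaplan-Meier limit, which for a = b reduces to exp(-at) × (1 + 0.7at)^(1/0.7): 0.125 × 2.455^1.429 = 0.451.
- With r = 1 the truth is 0.385, so the shift is +6.6 points.
- With r = 0.5, entrants' survival is 0.125 + (0.125 - 0.0156) = 0.234. The truth is 0.7 × 0.385 + 0.3 × 0.234 = 0.340, so the shift is +11.1 points. One binomial SE at n = 15 is √(0.340 × 0.660/15) = 0.122, so this is 0.91 SE; at n = 10 it is 0.74 SE.

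*Grid of 9,945 scenarios* (medians in steps of 0.25 month, p in steps of 0.05, r in steps of 0.125):

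| Entrants' status known until | Shift in 12-month OS, points |
|---|---|
| progression | -4.1 to +11.2 |
| 1 month after | -4.0 to +8.0 |
| 2 months after | -3.8 to +5.9 |
| 3 months after | -3.5 to +4.4 |

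With censoring at progression, the range is -1.5 to +3.4 points at 10% entering and -2.9 to +7.1 at 20%; the full range belongs to 30%. When entrants survive as long as others (r = 1), the shift is always upward, +0.7 to +6.6. In 86% of scenarios it is under 5 points, and in all of them it is below one SE at n = 15 (10.1-12.9 points). These shares describe the grid and are not probabilities; the ranges are not bounds.

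**The case against.** The best reply is that 4.6 states a general rule and then a specific exception, which Appendix D shows was added on purpose in Amendment 2. On that reading the exception governs, Section 7.2.2 only says how late deaths are classified, and footnote 11 merely needs aligning. A reader might call the passages a flat contradiction. That goes too far, since the exception reading is available. It does not restore the missing survival data, however, and copying the exception into footnote 11 would make the loss uniform.

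Three other stronger readings are tempting:

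- *OS is cut off at the date of entry.* Not established. Last follow-up can fall later, and treatment may continue until progression is confirmed or beyond it (Section 6.4), so entry at the instant of progression is an extreme case. The table shows how quickly the upper end falls.
- *OS will be overstated.* Not established. The sign depends on how entrants' prognosis compares with that of others.
- *The bias can never be checked.* Not established. A date of death or last known alive may be recoverable from records.

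It is also fair that the trigger evidence is thin, that the waiver is optional, and that OS has no stated test or power. At 10-15 patients per arm, sampling error exceeds every modelled shift. These points limit the weight of the concern without removing it.

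**Conclusion.** The concern holds as a cheap and worthwhile correction. The survival waiver in 4.6 departs from the all-patient rule in the same section and in footnote 11. Where used, it can censor OS informatively if entry follows progression. What is exposed is a secondary, descriptive Kaplan-Meier endpoint and the exploratory Cox analyses. The primary T-cell endpoint and the sample size are not affected.

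The only size that needs no assumption about entry or survival is the worst-case width of 1/n per lost patient. The modelled shifts rest wholly on the assumed inputs above; the three-month case also assumes that survivors' status, not only deaths, is recorded for that time. The documents settle neither size nor sign.

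The waiver also covers progression, and a reader might infer equal harm to time to progression. The documents leave that open: Section 10.3 counts early discontinuation of treatment as an event, which would close most such cases, but Sections 2.2.2 and 6.2 do not list it.

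**What to change.** - Delete the survival waiver from 4.6 so that the section agrees with its own general rule and with footnote 11.
- Follow vital status by the existing 8-16-weekly phone or record contact in every patient who has not withdrawn consent, including those in other trials. Section 4.7 permits no follow-up after withdrawal of consent.
- State in Section 10.3 that OS is not censored at new therapy or at entry to another study.
- Report, per arm, how many OS-evaluable patients have unknown survival status.
- Where the waiver has already been used, recover the date of death or last known alive from records where consent allows.

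The cost is a short text amendment and a few extra contacts on a schedule already planned, with no new visits or procedures. Section 4.6 already keeps patients who join another study under follow-up until their adverse events are resolved or stable.
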